8.2 Sample Size and Accrual

Prior studies and systematic reviews have shown participant standard deviations in daily steps of approximately 1300-1800 steps/day (20, 30, 32). Furthermore, previous studies measuring the impact of similar interventions on patient fitness levels have observed a patient step count change score standard deviation of approximately 1700 steps/day (29), where change score is defined as the change in step count from baseline to a particular week post-baseline. To determine whether there is a significant increase in physical activity among patients receiving the feedback messaging intervention versus those that do not receive the intervention, we will compare participant change scores between the each arm in our study. Assuming a participant change score standard deviation of 1800 steps/day, we estimate that 15 women will provide 80% power to detect a 2000-step difference in change score between arms (30), utilizing a two-sided Wilcoxon Two-Sample test with an alpha of 0.05. Within each arm, we will have sufficient power with $n = 15$ subjects to determine whether change scores within an arm are significantly different from zero, and we estimate that we will have >95% power to detect a change score of at least 2000 steps/day using a two-sided Wilcoxon Signed Rank test, assuming an alpha of 0.05 and a patient change score standard deviation of 1800 steps/day. We will also perform similar tests utilizing change scores computed at 4 weeks and 8 weeks post-baseline to determine whether these effects appear earlier on during the intervention period. We will also directly examine linear trends in daily step count with respect to time in days, as well as the overall three month average change in step count from baseline, via linear mixed models. Prior similar fitness intervention noted a 5% attrition rate in a large trial over 6 months time (29). To make a conservative estimate we will allow for 20% attrition and thus aim to enroll 39 total patients to obtain 36 evaluable datasets (18 patients in each arm). All power calculations were computing using G*Power software version 3.1.9.2 (33).

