CHART and Tailored Feedback. The Carolina Health Assessment and Resource Tool or CHART has been successfully utilized in a variety of settings to facilitate behavior change. CHART has available modules for wearable activity trackers, physical activity and weight. The modules provide users with individual assessment and tailored feedback to promote behavior change. Further, the CHART wearables module has been applied effectively to provide weekly tailored feedback in both AA men (iMOVEIt) and childcare providers (CARE2bFit). Both studies showed improved self-monitoring compliance and modest changes in physical activity. Men using wearables had about 600 more steps per day, while women in the CARE2bfit program increased their MVPA by 60% (12 to 20 minutes per day) through the middle three weeks of the study, but decreased back to week 1 levels as the program concluded. This tool has not been previously evaluated in EC patients, who appear highly motivated following their cancer diagnosis. Thus, *we propose a physical activity intervention in the EC survivor population, using weekly tailored feedback to increase steps per day using a wearable activity tracker.*

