8.0 STATISTICAL CONSIDERATIONS

8.1 Study Design

This is a randomized, single-center, tailored feedback message intervention trial. The project will use fitness trackers to measure increase in physical activity from baseline in women randomized to receive weekly motivational feedback messages. A control group will receive a fitness tracker but no feedback message reinforcement. The primary objective of the study is to detect a 2,000 mean daily step increase from baseline in patients undergoing the feedback message intervention. Therefore, patients will be randomized, 1:1 using a 6-block scheme.

Exploratory objectives include gathering data on the acceptability of the intervention, as well as desired frequency, timing, and content of messages for use in a larger trial. Additionally, outcomes that will be the goal of a larger trial will be explored. These endpoints include: BMI, waist/hip ratio, QOL as measured by FACT-G, and serum metabolic markers (fasting insulin, glucose, and LDL).

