8.3 Data Analysis Plans

Our primary objective will be measured by comparing patients baseline step counts (defined as the mean step count recorded by the fitness tracker for each participant in the first 7 days following enrollment) to week 12 (final week of study participation) step counts. The week 12 step counts will also be the mean step count recorded by the fitness tracker over 7 days in a participant's final week on the study. The

mean change in steps in the intervention group will be compared to the no-intervention group using a Wilcoxon Two-sample test.

For our exploratory objectives:

Acceptability of the intervention will be measured, as previously reported, using the results of a post-intervention Likert scale survey (29). At study conclusion, patients randomized to the feedback messaging arm will complete a post-intervention survey regarding the acceptability of the invention. Question #1 of the post-intervention survey will ask patients about the acceptability of the intervention using a 5-point Likert scale. The completion survey will also include information about desired frequency of messages, desired content of messages, and timing of messages. The information obtained in this portion of the study will allow improvements to be made in our intervention prior to implementation of a larger randomized trial. The acceptability of the intervention will be defined as the proportion of patients answering favorably (very helpful or somewhat helpful) to question #1 on the completion survey. We aim to have 80% acceptability. Previous surveys of adults have shown 81% to find mobile health interventions acceptable (34). We will report the proportion of subjects reporting favorable responses to question #1 on the completion survey and the corresponding 95% CI.

Finally, we will look for decrease in BMI, improved W/H ratio, improved QOL, and improved serum metabolic markers. These data will be preliminarily evaluated in this pilot study, but will represent the primary endpoints of interest in the randomized trial to be conducted following completion of this pilot. Basic descriptive and comparative statistics will be performed to evaluate BMI, QOL, W/H ratio and insulin/glucose/LDL levels as exploratory endpoints at each time point, in addition to the change in each exploratory endpoint between time points. All computed descriptive statistics would be stratified by study arm.

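### The mixed model describes the step-count course only as a straight line in days, which cannot show an effect that rises and then wears off, the pattern the protocol itself reports for an earlier CHART programme in women

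*Combined protocol and SAP*

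**What the plan says.** The primary analysis (section 8.3) compares the 7-day baseline mean with the final week. "The week 12 step counts will also be the mean step count recorded by the fitness tracker over 7 days", and the arms' changes are compared by a Wilcoxon two-sample test. This matches objective 2.1, which is change from baseline to 12 weeks.

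Section 8.2 adds three kinds of analysis: the same tests on change at 4 and 8 weeks, a linear trend ("We will also directly examine linear trends in daily step count with respect to time in days"), and, in the same sentence as the trend, the average change over the three months from linear mixed models. The stated purpose of the 4- and 8-week tests is to see whether effects arise sooner, not whether they fade. Section 8.3 does not repeat any of these analyses.

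In section 1.2 the protocol describes women in a programme that used the CHART wearables module. Their moderate-to-vigorous activity (MVPA) went from 12 to 20 minutes a day "through the middle three weeks of the study, but decreased back to week 1 levels as the program concluded".

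**The concern.** The protocol cites a rise-and-fall course and then gives the time course a form that can only go steadily up, steadily down or stay flat. A rise followed by an equal fall has no linear slope. Fading is not far-fetched here: the message library in Appendix 1 reuses earlier texts from week 6 on and lists next-week goals only for weeks 1 to 6.

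The study is a pilot meant to improve the intervention before a larger trial. Feedback that never worked and feedback that worked and then wore off call for different next designs, and the trend model as written would not tell them apart.

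**Working it through.** **1. The plan's own power figure.** Inputs from section 8.2: "Assuming a participant change score standard deviation of 1800 steps/day", a 2,000-step difference, and "utilizing a two-sided Wilcoxon Two-Sample test with an alpha of 0.05"; from section 8.1, 1:1 allocation.

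- Effect size: d = 2000/1800 = 1.11.
- Noncentral t with n multiplied by the Wilcoxon efficiency 3/π, at 15 per arm: 81.7%. Simulation of the exact Wilcoxon test: 80.6%.
- The plan says "we estimate that 15 women will provide 80% power to detect a 2000-step difference in change score between arms". This reproduces if 15 is read as per arm.
- With the planned 18 evaluable per arm, power for 2,000 steps held at week 12 is about 88%.

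**2. Slope of a rise-and-fall difference.** Assumed between-arm courses (not in the documents), each zero at weeks 1 and 12:

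- Triangle: linear up to 2,000 at week 6.5 and back; weekly values sum to 10,909.
- Plateau: up 500 a week to 2,000 in weeks 5–8, then down; values sum to 14,000.
- 2,000 in weeks 6–8 only, or in weeks 5–7 only; values sum to 6,000.

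Slope = Σ(w − w̄)·v / Σ(w − w̄)².

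- Weeks 1–12 (w̄ = 6.5, denominator 143). Triangle and plateau: 0 by symmetry. Weeks 6–8: 2000 × (−0.5 + 0.5 + 1.5)/143 = +21. Weeks 5–7: 2000 × (−1.5 − 0.5 + 0.5)/143 = −21.
- Weeks 2–12 (w̄ = 7, denominator 110). Triangle: −0.5 × 10,909/110 = −50. Plateau: −0.5 × 14,000/110 = −64. Weeks 6–8: 2000 × (−1 + 0 + 1)/110 = 0. Weeks 5–7: 2000 × (−2 − 1 + 0)/110 = −55.

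Units are steps/day per week. For comparison, a steady climb to 2,000 at week 12 has slope 2000/11 = 182. The documents do not say whether week 1 enters the model, so even the sign of the slope is open.

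**3. What each planned analysis would detect.** Simulated trials with 18 per arm, person SD 1,500 and independent weekly residual SD 1,273, so that the change-score SD is 1273 × √2 = 1,800. Controls are flat and tests are unadjusted at 0.05. The slope is tested per woman over weeks 1–12. Weeks 4 and 8 are counted with the baseline week as week 1.

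| Course | Mean gain, weeks 2–12 | Week 12 | Slope | Week 8 | Average | Week 4, week 8 or average |
|---|---|---|---|---|---|---|
| Triangle | 10,909/11 = 992 | 5% | 5% | 63% | 56–58% | about 75% |
| Plateau | 14,000/11 = 1,273 | 5% | 5% | 88% | 78–81% | 94% |
| Weeks 6–8 | 6,000/11 = 545 | 4–5% | 9% | 88% | 20–22% | 89% |
| Weeks 5–7 | 545 | test level | 9% (mirror image) | test level | as for weeks 6–8 | about 26% |

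In the last row the difference is zero at weeks 4 and 8, so both looks miss it.

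**4. Sensitivity.** A second set of runs used SD 1,800 each week, correlations of 0.5 to 0.9 between weekly change scores, and somewhat different shapes. The week-12 test again rejected in about 4–5%, the week-8 test in 70–88% and the average in 15–84%. The picture is stable for weeks 12 and 8. For the average it depends strongly on shape and correlation.

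**The case against.** The strongest reply is that the linear trend does not stand alone. The quoted sentence goes on to the three-month average, and the sentence before it plans the 4- and 8-week tests. That is right. A reader might infer that a fading effect would make the whole trial read as no effect. The documents do not support that inference: for three of the four courses above, at least one of the other planned analyses is significant in about 75–94% of trials.

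A reader might also infer that week 12 is the wrong primary time point. It is not. Objective 2.1 asks about change to 12 weeks, and an effect gone by then should give a null there.

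Nor does the precedent carry over directly. It concerns MVPA minutes rather than steps, and section 1.2 reports neither a comparison arm nor a programme length. If the tracker-only controls here decline, a week-12 difference could remain. The protocol says only that the CHART module was applied in that programme, so it should not be called the sponsor's own study.

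Finally, a negative slope over weeks 2–12 might be said to reveal the fading. Taken alone, it does not distinguish an early gain being lost from a fall below the control arm, and for a gain in weeks 6–8 it is zero.

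What remains after all this is the form of the trend model and the gap between the two intermediate looks.

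**Conclusion.** The concern holds for the trend model. A slope in days is near zero for a rise-and-fall course when week 1 is included (0 for symmetric shapes, about ±21 for a three-week gain) and zero to about −64 when it is not. It therefore cannot separate no effect from an effect that wore off. The other planned analyses cover much of the gap but not all of it: detection falls to about 26% for a gain confined to weeks 5–7. If 4 and 8 weeks are counted from the end of the baseline week, the looks move one week later and the blind interval moves with them.

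These figures rest on an assumed 2,000-step peak, a zero difference at week 12, flat controls and the plan's SD of 1,800. They show what could be missed, not what is expected. The primary test is not in question.

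**What to change.** In the mixed model already planned in section 8.2, use weekly mean steps with week as a categorical factor and an arm-by-week interaction. Keep the linear trend at most as a supplement, and say whether week 1 enters it. Report the between-arm difference for each week with a 95% CI beside the three-month average, and list both in section 8.3. State in advance that a null at week 12 with a clear earlier difference will be described as an effect not sustained. Week 12 stays primary.

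Promoting the three-month average to a key secondary endpoint is optional. It has only about 20–22% power for a three-week gain, so it would not close the gap by itself.

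The change needs only analysis-plan wording, since daily steps are already collected. Its price is more parameters (11 interaction terms over 12 weeks) and imprecise weekly estimates. With 36 women the standard error of one week's difference in change is about 1800 × √(2/18) = 600 steps, a 95% interval of roughly ±1.96 × 600 = ±1,176. The weekly results should therefore be labelled supportive.

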PROTOCOL AMENDMENT #3

LCCC 1614: The MOVES Trial: MOTiVating Endometrial Cancer Survivors with Activity Monitors and Tailored Feedback

AMENDMENT INCORPORATES (check all that apply):

Editorial, administrative changes
 Scientific changes (IRB approval)
 Therapy changes (IRB approval)
 Eligibility Changes (IRB approval)

AMENDMENT RATIONALE AND SUMMARY:

This amendment increases the accrual from 36 to 39 participants to account for participants who did not complete the study and ensure enough evaluable data is collected to meet the aims of the study.

1. We updated Section 1.1 to justify accrual from 36 to 39 patients.
2. Section 4.0 graphics was updated to show new accrual goal.
3. Section 5.0 was also updated to justify new accrual goal
4. We are changing the PI from [name] MD to [name] MD

PROTOCOL AMENDMENT #2

LCCC 1614: The MOVES Trial: MOTiVating Endometrial Cancer Survivors with Activity Monitors and Tailored Feedback

AMENDMENT INCORPORATES (check all that apply):

Editorial, administrative changes
 Scientific changes (IRB approval)
 Therapy changes (IRB approval)
 Eligibility Changes (IRB approval)

AMENDMENT RATIONALE AND SUMMARY:

This amendment adjusts timing of consent and enrollment visits to minimize the time lapse in between these two occurrences (~3 months). After careful review, waiting about three months between consent and enrollment can askew data and cause patient behavioral changes.

1. Edited exclusion criteria in section 3.2.2 to exclude patients with no computers or Bluetooth capabilities as those are required for the study.
2. Edited schema in section 4.1 and changed “Day on enrollment” to “Baseline Visit”
3. Edited section 4.2 to include:
 - a. The possibility of contacting physician-identified patient’s via telephone to assess interest and obtain verbal consent.
 - b. In-person interactions will now allow coordinator to approach possible subjects to introduce the study prior to consent
 - c. A third phone call to remind patient of fasting prior to the post-intervention visit
 - d. Clarification that all subjects will now receive reminder emails to sync Fitbit and log into UNC CHART
4. Edited section 4.3 to reflect re-adjustment of timing of consent & enrollment visits so these can occur on the same day.
5. Removed mentions of GPAQ show cards and Appendix 2 and 3 in the protocol (section 4.3 and section 5.1)

PROTOCOL AMENDMENT #1

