1.0 BACKGROUND AND RATIONALE

1.1 Study Synopsis

Overweight and obese endometrial cancer (EC) survivors at UNC-CH will be approached for tailored feedback fitness intervention. We aim to enroll 36 evaluable women (18 in each arm) to evaluate if receipt of weekly tailored feedback messages can improve physical activity in EC survivors. We anticipate enrolling 39 participants to be able to evaluate 36. We hypothesize women receiving the feedback message intervention will increase step counts from baseline more than 2,000 steps compared to women in the non-intervention arm.

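### Section 8.2: a 20% attrition allowance, 39 enrolled and 36 evaluable cannot all hold; 20% loss from 39 leaves about 31, and 36 would need 45

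*Combined protocol and SAP*

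**What the plan says.** Section 8.2 (Sample Size and Accrual) cites 5% attrition over 6 months in an earlier large trial, chooses a more cautious rate, and derives the accrual from it: "To make a conservative estimate we will allow for 20% attrition and thus aim to enroll 39 total patients to obtain 36 evaluable datasets". The evaluable total is meant as 18 per arm.

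Section 1.1 repeats the pair without a rate: "We anticipate enrolling 39 participants to be able to evaluate 36". Section 5.0 (Schema) also gives 39 enrolled for 36 evaluable, again without a rate.

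The rationale for Amendment #3 gives the reason for 39: "This amendment increases the accrual from 36 to 39 participants to account for participants who did not complete the study".

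The power statement in Section 8.2 uses a smaller number: "we estimate that 15 women will provide 80% power to detect a 2000-step difference in change score between arms". The following sentence of 8.2 applies n = 15 within each arm, so the figure is per arm, 30 in total.

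**The concern.** Section 8.2 presents 39 as the result of applying a 20% allowance to 36 evaluable women. It is the only place that attaches an attrition rate to the accrual target, so it is the only justification a reader can check, and it does not compute.

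A reader will take it that 36 evaluable women survive a cautious 20% loss. In fact the fourth loss already misses 36. The real margin for 36 is much closer to the 5% seen in the earlier trial than to the 20% the plan says it chose. The question is then whether the powered sample size is at risk as well.

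**Working it through.** **Inputs.** From Section 8.2: attrition 20%; enrolment 39; evaluable target 36; 15 per arm for 80% power; difference 2000 steps/day; SD of change 1800 steps/day; two-sided Wilcoxon two-sample test, alpha 0.05. From Section 8.1: 1:1 allocation with a block scheme of 6.

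**1. Can 39 be reproduced?**
- Standard inflation, n/(1 − d): 36/0.80 = 45.
- Looser convention, n × (1 + d): 36 × 1.2 = 43.2, so 44.
- Forward: 39 × 0.80 = 31.2.
- Loss implied by 39 to 36: 3/39 = 7.7%.
- At the cited 5%: 36/0.95 = 37.9, so 38.

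Neither convention gives 39 at 20%.

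**2. Does the powered size survive 20% loss?**
- Enrolment needed for 30 evaluable: 30/0.80 = 37.5, so 38. The planned 39 covers this.
- Loss that 39 tolerates before falling below 30: 9/39 = 23.1%.

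**3. Power.** The standardised difference is 2000/1800 = 1.11. Power was computed by noncentral t, with sample sizes scaled by the Wilcoxon test's efficiency relative to the t-test: 3/π for normal data, 0.864 as the worst case.

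| Evaluable per arm | Normal data | Worst case |
|---|---|---|
| 15 + 15 | 81.7% | 77.4% |
| 15 + 16 | 83.0% | 78.8% |
| 14 + 17 | 82.7% | 78.5% |
| 18 + 18 | 88.5% | 85.0% |

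The plan's 80% with 15 per arm is therefore reproduced under normal data. Exact Mann-Whitney simulation with normal data (20,000 runs) agrees: 80.8%, 82.7%, 82.1% and 87.8%. In the worst case, 80% needs 16 per arm. Reading the 15 as a total (7 + 8) would give only 49%, which confirms that it is per arm.

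**4. Chance of reaching each target from 39**, assuming independent loss at 20%:
- at least 36 evaluable: 3%;
- at least 30 evaluable: 76%;
- at least 15 in both arms: 54% from a 19/20 split, 45% from an 18/21 split.

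An odd total cannot divide equally. If the scheme means blocks of six, 39 fills six blocks and half of a seventh. The last three assignments then usually fall 2–1 (19/20); they fall 3–0 (18/21) with probability 2/C(6,3) = 2/20 = 10%.

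**5. Is 18 per arm assured with exactly 3 losses?** From 19/20, three random losses leave 18/18 with probability C(19,1)·C(20,2)/C(39,3) = 39.5%. From 18/21 it is C(21,3)/C(39,3) = 14.6%. This barely affects power: 17 + 19 gives 88.4%.

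**The case against.** The strongest reply is that this is a leftover phrase rather than a planning error. Accrual was 36 before Amendment #3, and 30 × 1.2 = 36, so the 20% may once have linked the powered 30 to an accrual of 36. The superseded text is not available, so this is inference. Measured against 30, the present 39 does absorb a 20% loss. This is a fair reason to rate the point as minor, but it does not rescue the current sentence, which ties the 20% to 36 evaluable women. On this reading, too, the sentence must be rewritten.

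A second objection is that the 54% and 45% treat 15 per arm as a cliff. Under the same normal-data calculation, 14 + 15 gives 80.3% and 13 + 18 gives 82.1%. Counting every loss pattern, the chance that power stays at or above 80% is 81% from 19/20 and 79% from 18/21, with average power about 83%. This stands as a matter of emphasis: missing 15 in one arm costs little power. The 14 + 15 case is borderline, since exact simulation puts it at 79.2%.

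Third, the binomial figures assume independent 20% loss in all 39 women, although Amendment #3 responds to non-completion already seen and gives no count. That is so. The figures show how thin the margin is; the contradiction does not depend on them.

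**Conclusion.** The concern holds: Section 8.2 is wrong as written. With 39 enrolled, 20% attrition leaves about 31 evaluable women, 5 short of 36. Keeping both 20% and 36 would take 45 enrolled, 6 more than planned. The contradiction is pure arithmetic and needs no assumption. It lies in the current text of 8.2; Sections 1.1 and 5.0 state no rate, and the amendment rationale is context only.

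The impact is minor. The stated 80% power needs 30 evaluable women, and the 31 expected after 20% loss exceed this by about one. That is an expected value and not a guarantee. The power figures of about 82–83% at 31 evaluable and about 88% at 36 assume normally distributed change scores. With the least favourable distribution they fall to about 78–79% and 85%.

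**What to change.** Keep 39 enrolled and replace the attrition sentence in Section 8.2 with wording such as:

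> Enrolment will be 39 patients. This gives 36 evaluable datasets in total (about 18 per arm, about 88% power) if no more than 3 women (7.7%) are lost. If 20% were lost, about 31 evaluable women would be expected (about 82–83% power), against the 30 (15 per arm) needed for 80% power. These power figures assume normally distributed change scores for the Wilcoxon test.

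The sponsor should confirm that the distributional assumption matches the setting used in its own power software, which Section 8.2 does not state, and adjust the percentages if it does not.

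Two optional wording changes would help: add that the 15 women in the power statement are per arm, and in Section 5.0 present 36 evaluable as a target rather than as assured.

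The cost is one short passage in 8.2. No patients are added and no test or endpoint changes. The drawback is that the stated allowance for 36 evaluable falls from 20% to 7.7%, which is what 39 already delivers. Keeping 20% for 36 would cost 6 more patients, which the 80% power statement does not require.
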